### ***Definition of Primary and Secondary Outcomes/Endpoints***

Because qualitative research is by nature exploratory, we have not defined outcomes for the focus group discussions with practice staff (**Aim 1**); however, we will use the Promoting Action on Research Implementation in Health Services (PARIHS) framework to guide these discussions about facilitators and barriers to WE CARE implementation. Key areas of exploration will be (1) evidence: attitudes and beliefs about evidence of the WE CARE system; (2) context: organizational, systemic, and sociopolitical features that promote or hinder implementation of WE CARE; and (3) facilitation: attributes of the facilitation that supported or impeded the implementation, and needed adaptations.

Primary outcomes for **Aim 2** include the following:

- *Identification of unmet needs and provision of referrals.* Previously utilized forms will be used during baseline and follow-up questionnaires to measure whether practitioners provided families resource handouts.
- *Parental enrollment in community-based resources.* Baseline and follow-up questionnaires to measure enrollment in community resources.
- *Process measures.* Data will be collected on adherence to clinic visits (appointments kept, cancelled, and no-show). We will collect data on medications adherence in two ways. First, we will collect laboratory markers that are commonly affected by HU, including hemoglobin and hemoglobin F levels, white blood cell and absolute neutrophil counts, and MCV. We will also collect data on prescriptions written and filled for HU and penicillin through EHR review and parent report.
- *Health outcomes:* Data on vaso-occlusive episodes, acute chest syndrome and sepsis will be collected from the EHR at 6-month- and 12-month follow-up. Quality of life will also be assessed through both the PedsQL, which has been validated in children with sickle cell disease and is responsive to change, and the PedsQL Sickle Cell Disease Module.
- *Healthcare utilization outcomes:* Data on emergency department visits, hospitalizations, and clinic visits will be collected from the EHR at baseline and 12-month follow-up. We have chosen

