emergency department visits as our primary outcome because it has been extensively, and commonly, used as a measure of lack of outpatient care and non-adherence to treatment regimens in this population. We will also calculate ED reliance (clinic visits kept / clinic visits kept + ED visits), as it has been used to discriminate frequent emergency department users.

Because qualitative research is by nature exploratory, we have not defined outcomes for the qualitative interviews with parents of children with SCA (**Aim 3**). Qualitative interviews will aim to examine parents' perceptions of factors that promote or hinder effective management of their child's SCA.

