***Aim 2. Obtain population-specific empirical estimates of study parameters to plan a pragmatic large-scale cluster RCT.*** We will summarize the number of parents contacted, lost to follow-up, refusing participation, and enrolled. We will examine this by gender (e.g., father vs. mother). We will note reasons for refusals. We will determine parents' recruitment and attrition rates and receipt of WE CARE using descriptive statistics. We will also determine the data collection completion rate, including hair cortisol, for each data time point (baseline, 3-, 6-, 9-, and 12-month follow-up) via descriptive statistics. Each outcome and process variable described above will be first transformed into its final composite value/score. We will calculate within-group mean and standard deviation of our SDoH, process, mediator and health utilization and health outcome variables. We will also break down the intervention group into two subgroups differentiated by whether parents enrolled in resources at follow-up, and explore any differences. An intention-to-treat approach will be used to explore differences between the intervention and control groups. We will also report all data disaggregated by gender. Two independent sample t-test and chi-square tests will be used to determine bivariate differences. Mixed effects regression models will be used to estimate the effect size of the intervention on SCA outcomes accounting for baseline differences in sociodemographics, types of SDoH, cumulative needs, receipt of services, and *a priori* determined covariates (i.e. sociodemographic characteristics). To explore potential moderators for the intervention effect at the parent, child and family levels (e.g., gender, race, ethnicity, age, language, household income), we will use Rothman's methodology; specifically, we will conduct stratified analyses for each potential moderator followed by using standard interaction terms in our models. We will also explore mediation of our hypothesized potential mediators between SDoH and the intervention with each SCA health outcome using the approach recommended by MacKinnon, Lockwood, and Williams. We will account for the clustering by study site by calculating the intraclass correlation.

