## Statistical Power and Sample Considerations

We will enroll up to 235 subjects in this study, including up to 60 practice staff and 175 parents of children with SCA.

Because the goal for **Aim 1** is to examine the implementation of WE CARE in the outpatient pediatric hematology clinical setting our sampling will be purposeful. Based on our previous experience, we anticipate up to 15 practice staff per site will participate in focus group discussions.

For **Aim 2**, we are proposing to enroll 35 families from each of the four study sites (2 experimental, 2 control) to field test study logistics, including collecting empiric estimates of study parameters for a larger pragmatic trial. To demonstrate the feasibility of our study design, we use ED visits (primary

outcome) and penicillin adherence as examples. Assuming a 5% error rate, and based on our R00 WE CARE study, we expect a cluster coefficient no larger than 0.01. Based on recent data, we expect at least 80% of children in our control group to have at least one ED visit within our study observation period. We expect that our intervention group will have a much lower proportion, with ≤40% having with one or more ED visits. Our proposed study sample has >90% power to detect differences of at least 25% in the proportion of children with ED visits. In addition, based on estimates from the literature we expect a 9-month medication adherence of 40% and 10% in the intervention and control groups, respectively. Our study will have 90% power to detect differences of at least 20% in penicillin adherence, which is considered clinically significant. Consistent with CONSORT guidelines for pilot studies, we will not use results from this study to determine efficacy, since effects sizes from pilot studies likely overestimate or underestimate the true effect size; rather we will determine empiric estimates from the control group as the basis for power calculations for a future multi-site trial.

For **Aim 3**, in order to explore an array of beliefs and practices regarding family contextual factors that promote or prevent effective SCA management, enrollment will continue until saturation is reached (i.e. more interviews will not generate additional information) in primary research questions. Based on our previous experience, we expect 25-35 parents will be sufficient to reach saturation.

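### The Aim 2 primary outcome is not singular, and the named one (ED visits) is defined only as any versus none in the sizing example, with no stated model family or adjustment for baseline ED visits

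*Combined protocol and SAP*

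**What the plan says.** **Which outcome is primary.** The section Definition of Primary and Secondary Outcomes/Endpoints opens its list with "Primary outcomes for Aim 2 include the following" and gives five domains: needs and referrals, enrollment in resources, process measures, health outcomes, and healthcare utilization. Inside the last domain it chooses "emergency department visits as our primary outcome because it has been extensively, and commonly, used". The section Statistical Power and Sample Considerations again labels ED visits the primary outcome. No outcome is labelled secondary.

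**What is collected.** "Data on emergency department visits, hospitalizations, and clinic visits will be collected from the EHR at baseline and 12-month follow-up". The number of visits is needed anyway, because "We will also calculate ED reliance (clinic visits kept / clinic visits kept + ED visits").

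**How it is sized.** At least 80% of controls and at most 40% of the intervention group are expected to have one or more ED visits, the cluster coefficient is at most 0.01, and "Our proposed study sample has >90% power to detect differences of at least 25% in the proportion of children with ED visits". The text offers this as an example of feasibility and says that the pilot will not be used to determine efficacy.

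**How it is analysed.** The Data Analysis Plan for Aim 2 gives means and standard deviations of the utilization variables, then: "Two independent sample t-test and chi-square tests will be used to determine bivariate differences". Mixed effects regression follows for the effect size, with no family or link named. Its covariates are sociodemographics, types of need, cumulative needs and receipt of services. Baseline ED visits are not among them.

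**The concern.** Three things are left open for the outcome that the protocol itself singles out: whether it is the only primary outcome, whether it is a count or a yes/no variable, and which model estimates the effect.

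The one form that is written down is a poor one for this population. If four in five control children already have a visit, a child who goes from six visits to one registers no change on any/none. The pilot exists to supply planning estimates. A future trial on ED visits would need the control-arm rate, its overdispersion and the site correlation, and the plan does not commit to reporting the first two. The prior ED count, an obvious candidate for a strong predictor of later ED use, is collected at baseline but not used in the model.

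**Working it through.** **Inputs from the documents (Statistical Power and Sample Considerations)**
- "we are proposing to enroll 35 families from each of the four study sites (2 experimental, 2 control"): 70 per arm, two sites per arm.
- "Assuming a 5% error rate": sidedness is not stated; two-sided is used below unless noted.
- ICC 0.01. Control any-visit proportion 80%. A 25-point difference gives 55%; the expected difference gives 40%.

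**Inputs assumed.** The documents give no ED rate or dispersion. Counts are taken as Poisson (k = 0) or negative binomial with variance μ + kμ², k = 0.5 or 1.

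**Step 1. The protocol's own power figure.**
Design effect = 1 + 34 × 0.01 = 1.34; effective n = 70/1.34 = 52.2 per arm.
- Null SE (mean proportion 0.675) = √(2 × 0.675 × 0.325/52.2) = 0.0916.
- Alternative SE = √((0.80 × 0.20 + 0.55 × 0.45)/52.2) = 0.0883.
- Pooled: Φ((0.25 − 1.96 × 0.0916)/0.0883) = Φ(0.80) = 79%.
- Unpooled: Φ(0.25/0.0883 − 1.96) = Φ(0.87) = 81%.
- One-sided: 87%.
- With no design effect: 89% pooled, 91% unpooled, 94% one-sided.

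So >90% appears only if the stated ICC is dropped, or if the control proportion is well above 80% (95% v 70% gives 93% with ICC 0.01). At the expected 80% v 40%, power is 99%.

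**Step 2. Mean counts implied by the proportions.** Poisson: μ = −ln(1 − p). Negative binomial: μ = ((1 − p)^(−k) − 1)/k.

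| | 80% | 55% | 40% |
|---|---|---|---|
| Poisson | 1.609 | 0.799 | 0.511 |
| k = 0.5 | 2.472 | 0.981 | 0.582 |
| k = 1 | 4.000 | 1.222 | 0.667 |

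**Step 3. Information on the log rate.** Variance per child from a count is 1/μ + k. From any/none it is p(1 − p)/D², where D = μ(1 − p) for Poisson and μ(1 + kμ)^(−1/k − 1) for negative binomial. Information lost on the contrast is 1 − (sum of count variances)/(sum of any/none variances).

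| Contrast | Distribution | Count | Any/none | Lost |
|---|---|---|---|---|
| 80% v 55% | Poisson | 0.621 + 1.252 | 1.544 + 1.917 | 46% |
| | k = 0.5 | 0.905 + 1.519 | 3.273 + 2.820 | 60% |
| | k = 1 | 1.250 + 1.818 | 6.250 + 4.040 | 70% |
| 80% v 40% | Poisson | 0.621 + 1.958 | 1.544 + 2.555 | 37% |
| | k = 0.5 | 0.905 + 2.218 | 3.273 + 3.280 | 52% |
| | k = 1 | 1.250 + 2.500 | 6.250 + 4.167 | 64% |

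**Step 4. Power with counts at 80% v 55%, same ICC of 0.01.** Power = Φ(ln(μ₁/μ₂)/√(variance sum/52.2) − 1.96).
- Poisson: 0.700/√(1.873/52.2) = 0.700/0.189; Φ(1.74) = 96%.
- k = 0.5: 0.924/√(2.424/52.2) = 0.924/0.215; Φ(2.33) = 99%.
- k = 1: 1.186/√(3.068/52.2) = 1.186/0.242; Φ(2.93), above 99%.

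**Step 5. Why Step 4 is an upper bound.** Suppose site variation acts on the log rate and produces ICC 0.01 for any/none in controls. The site variance is then 0.01 × the control any/none variance in Step 3, and the count ICC is that variance divided by itself plus the control count variance.
- Poisson: 0.0154/(0.0154 + 0.621) = 0.024.
- k = 0.5: 0.0327/(0.0327 + 0.905) = 0.035.
- k = 1: 0.0625/(0.0625 + 1.250) = 0.048.

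With 1 + 34 × ICC as design effect (about 1.8, 2.2 and 2.6), effective n is about 38, 32 and 27 per arm, and the Step 4 formula gives about 89%, 92% and 94%. These still use a normal approximation. With two sites per arm, a site-level t-test on 2 degrees of freedom has only about 36% power for any/none at 25 points, and counting visits does not remove that limit.

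**The case against.** The case for leaving the plan alone has real parts.

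- **Any/none is only the sizing example.** A reader might infer that ED visits will be dichotomised in the analysis. The documents do not say so: the Data Analysis Plan reports means and standard deviations of utilization variables, and ED reliance uses visit numbers. This stands; the fault is that the form is unspecified.
- **More than t and chi-square tests are planned.** Those two are for bivariate differences. The effect size is to come from mixed models, so only the family, link and baseline adjustment are missing.
- **Rate and dispersion may be recoverable.** If counts are summarised, the mean gives the rate, and (SD² − mean)/mean² gives a moment estimate of k. A reader might infer that the pilot cannot supply these; it can, but the plan does not promise it.
- **The loss depends on assumptions.** It would be too strong to say that any/none discards most of the information. That is so for the control arm alone (60% Poisson, 80% at k = 1). For the contrast it needs assumed overdispersion.
- **The stakes are limited.** The pilot disclaims efficacy, and at 80% v 40% any/none already has about 99% power by the protocol's own method. EHR review is at fixed times, so unequal follow-up cannot be presumed.

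None of this resolves the two descriptions of what is primary, fixes the endpoint's form, or brings in the baseline count.

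**Conclusion.** The point holds in a limited form and is worth correcting before analysis. The text contradicts itself on whether Aim 2 has five primary domains or one primary outcome. The named outcome has no fixed form, no model family and no adjustment for its own baseline.

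Should any/none be carried into the analysis, the loss on the treatment contrast is about 37–46% (Poisson) or 52–70% (k = 0.5–1). Power at 80% v 55% would be about 79–81%, against roughly 96% or more for counts at a common ICC of 0.01, or about 89–94% if the count ICC is larger as in Step 5. The dispersion values, the log-rate site model and the two-sided test are assumptions.

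Separately, the >90% claim is not reproduced at the protocol's own ICC and 80% control proportion.

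A reader might go further and conclude that the five primary domains show an intent to choose the headline result afterwards. The documents show only that the wording permits it, in a pilot that says it will not judge efficacy.

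**What to change.** 1. Name the 12-month ED-visit count as the single Aim 2 primary outcome and label the other domains secondary.
2. Estimate the effect with a count mixed model, for example negative binomial, with an offset for observed time if that differs between children, adjusted for the baseline ED count. State the look-back period for that baseline count.
3. Report the control-arm rate, dispersion and ICC with intervals as the planning output. With so few sites the ICC interval will be wide, and the report should say so.
4. Keep the any-visit proportion as a descriptive result.
5. Restate the power sentence: about 79–81% two-sided for 80% v 55% at ICC 0.01, or give the assumptions that yield more than 90%.

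The cost is wording in the outcomes, analysis and power sections; no new outcome data are needed. The one drawback is that a rate ratio is less familiar than a percentage, so both should be shown.

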## Design and Methods

### *Study Design*

#### ***Study 1 (Aim 1): The implementation of a practice-based social determinants of health screening and referral intervention in two pediatric hematology clinics to field test key study logistics and understand the facilitators and barriers to implementation and accelerate its adoption***

Two of our four proposed pediatric hematology clinical sites will be randomized to implement WE CARE as standard of care for SCA patients. At baseline and every six months throughout the study period, the Boston Medical Center-based team (hereafter termed the core research team) will conduct focus

groups with stakeholders (e.g., clinical and administrative staff) at each of the four pediatric hematology clinic sites to better understand the barriers and facilitators to implementation of WE CARE. The site PI at each institution will help us identify staff members. Before beginning each focus group, the Boston Medical Center PIs and members of their research team will meet with clinic stakeholders at their staff meetings and provide an overview of the study. The Boston Medical Center-based team will conduct focus groups with pediatric hematology clinic staff every six months throughout the study period.

***Study 2 (Aim 2): Obtaining population-specific empirical estimates of study parameters to plan a future large-scale cluster RCT of WE CARE for children with SCA***

For this study, we will be conducting a pilot cluster RCT. Two of our four proposed pediatric hematology clinical sites (Boston Children's Hospital, Connecticut Children's Medical Center, Hasbro Children's Hospital (HCH) and Yale-New Haven Children's Hospital) will be randomized to implement WE CARE as standard of care for SCA patients. To assign the sites to either the control or the intervention group, we will first fix the number of sites to each group (i.e. 2 sites per group) and then assign sites to group using the random function for the uniform distribution in SAS 9.4.

***Study 3 (Aim 3): Qualitatively assess possible mechanisms linking SDoH interventions to improved health outcomes, such as increasing a parent's ability to manage their child's disease through medication adherence***

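### The >90% and 90% power figures for Aim 2 are not delivered by a four-site cluster design at the plan's own rates and cluster coefficient

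*Combined protocol and SAP*

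**What the plan says.** Under Study Design, Aim 2 is described thus: "For this study, we will be conducting a pilot cluster RCT". On allocation: "we will first fix the number of sites to each group (i.e. 2 sites per group").

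Statistical Power and Sample Considerations gives the sample, "we are proposing to enroll 35 families from each of the four study sites (2 experimental, 2 control"), and the assumptions: "Assuming a 5% error rate, and based on our R00 WE CARE study, we expect a cluster coefficient no larger than 0.01". For ED visits, "we expect at least 80% of children in our control group to have at least one ED visit within our study observation period", with at most 40% expected in the intervention group. For penicillin, the expected adherence is 40% with the intervention and 10% in controls. Two power statements follow: "Our proposed study sample has >90% power to detect differences of at least 25% in the proportion of children with ED visits" and "Our study will have 90% power to detect differences of at least 20% in penicillin adherence, which is considered clinically significant".

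The section does not state the sidedness of the 5% error rate, the formula, a design effect or any degrees of freedom. It presents the figures as examples to show feasibility, and says the pilot results will not be used to determine efficacy.

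The Data Analysis Plan for Aim 2 lists two-sample t-tests and chi-square tests, then: "Mixed effects regression models will be used to estimate the effect size of the intervention on SCA outcomes". It says clustering by site will be handled by calculating the intraclass correlation. It names no degrees-of-freedom method.

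**The concern.** Whole sites are randomised, so the effective sample is smaller than 140 children, and only four units carry the comparison. The stated powers look like those of a trial that randomised children individually, at least for ED visits. Two things could pull the true figures down: the cluster coefficient that the plan itself assumes, and the small number of sites.

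The paragraph is the only quantitative support for four sites of 35 families. Aim 2 exists to plan a larger cluster trial, so the way power is reasoned here may be carried forward. A reader who takes the 90% figures at face value could also read too much into a pilot comparison that shows no difference.

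**Working it through.** **Inputs from the plan.** 35 families at each of 4 sites, so n = 70 per group; 5% error rate; cluster coefficient at most 0.01; control rates of 80% (ED visits) and 10% (penicillin); differences of 25 and 20 points. The comparisons implied are 80% vs 55% and 10% vs 30%.

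**Assumptions added here.** Control rates exactly as stated, adherence as a yes/no outcome, no attrition, and all 35 children per site contributing to both outcomes. Sidedness is not stated, so both are shown.

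**Step 1: the plan's figures without clustering.** The unpooled standard error is SE = sqrt{[p1(1-p1) + p2(1-p2)]/n}, and power is Φ(difference/SE - z). The pooled version uses the average rate in the critical-value term.
- ED: SE = sqrt[(0.16 + 0.2475)/70] = 0.0763; 0.25/0.0763 = 3.28. Two-sided: Φ(3.28 - 1.96) = 90.6% (pooled 89.3%).
- Penicillin: SE = sqrt[(0.09 + 0.21)/70] = 0.0655; 0.20/0.0655 = 3.05. Two-sided: 86.3% (pooled 84.9%). One-sided: 92.1% (pooled 91.2%).

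So the ED figure is met, or nearly so, by a two-sided test that ignores clustering. The penicillin figure is met only by a one-sided test that ignores clustering.

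**Step 2: with the plan's cluster coefficient.** Design effect = 1 + (35 - 1) × 0.01 = 1.34. Effective n = 70/1.34 = 52.2 per group. The ratios in Step 1 are divided by sqrt(1.34), giving 2.83 and 2.64.

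**Step 3: allowing for only four sites.** If the arm effect is tested against variation between site results, there are 4 - 2 = 2 degrees of freedom. The 5% critical value is 4.30 two-sided (not 1.96) and 2.92 one-sided (not 1.645). Power comes from a noncentral t distribution with those ratios as noncentrality: 2.83 to 3.28 for ED and 2.64 to 3.05 for penicillin, for a coefficient of 0.01 to 0.

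| Basis | ED 80% vs 55% | Penicillin 10% vs 30% |
|---|---|---|
| Stated in the plan | >90% | 90% |
| Large-sample, no clustering, two-sided | 89-91% | 85-86% |
| Large-sample, no clustering, one-sided | 94-95% | 91-92% |
| Large-sample, coefficient 0.01, two-sided | 79-81% | 73-75% |
| Large-sample, coefficient 0.01, one-sided | 87-88% | 83-84% |
| 2 df, coefficient 0.01 to 0, two-sided | 36-44% | 32-40% |
| 2 df, coefficient 0.01 to 0, one-sided | 58-68% | 54-63% |

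Large-sample ranges run between the pooled and unpooled versions. Simulation of a two-sided t-test on the four site proportions agreed with the 2-df rows: 36-44% for ED and 34-41% for penicillin.

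**Step 4: sensitivity.**
- *Higher control ED rate*, which the plan's wording allows. For 95% vs 70% at coefficient 0.01, large-sample two-sided power is 93-95%, so the stated figure is reached. On 2 df, coefficient 0.01 to 0, it is 49-58% two-sided and 73-82% one-sided.
- *Fewer children on penicillin.* The Inclusion Criteria admit children aged 0-12 on penicillin or hydroxyurea, and the Background describes antibiotic prophylaxis until age 5. If, as an assumption, 15 to 20 children per site take penicillin, two-sided 2-df power is about 20-27%.
- *Attrition.* With 20% loss at coefficient 0.01, two-sided ED power falls to about 72% (large-sample, pooled) or 32% (2 df).

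**The case against.** The strongest reply is that the 2-df test is not the plan's. The Data Analysis Plan specifies child-level tests and mixed models without a degrees-of-freedom method, and the power section relies on an external bound for the cluster coefficient. Under that premise, a z-test using the fixed design effect of 1.34 behaves acceptably for ED visits. In simulation it held 5.0% type I error with 79% power at a coefficient of 0.01, and 2.3% with 83% power at zero. This stands, and it means that 36-44% cannot be presented as the power of the planned analysis. It does not rescue the printed figure, since 79% is not above 90%. It also holds only if the bound is right, because four sites can barely check it. A child-level test that ignores clustering would have about 9% type I error at a coefficient of 0.01: 2 × [1 - Φ(1.96/sqrt(1.34))].

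A second reply is that a control ED rate above 80% is permitted. That also stands for ED visits on the large-sample basis, at a rate near 95%. Penicillin has no such escape at its stated 10% control rate.

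A third is that this is a pilot with efficacy conclusions disclaimed. That limits the consequence, but does not make a stated power correct.

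Three stronger readings are tempting and are not supported:
- *Both figures come from a two-sided formula for individually randomised children.* No formula is given, and penicillin does not match two-sided.
- *The trial is underpowered even at its expected ED effect of 80% vs 40%.* On 2 df this gives 66-76% two-sided but 88-94% one-sided, and over 99% on the large-sample basis at coefficient 0.01.
- *The future trial will be sized on families.* The plan says only that control-group estimates will feed its power calculation.

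**Conclusion.** The point holds. At the implied rates, with 35 children per site and no attrition, the plan's own cluster coefficient of 0.01 puts both figures below what is stated, whichever side convention is used. The shortfall is about 10 points for ED visits and 15 to 17 for penicillin two-sided, and about 2 to 3 and 6 to 7 one-sided. These are the smaller, firmer numbers, and they still lean on an assumed coefficient and a normal critical value.

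The larger shortfall, to 36-44% and 32-40% two-sided or 58-68% and 54-63% one-sided, depends on a 2-df test. That test is a reasonable inference from randomising two sites against two, but the plan does not specify it. At a coefficient of exactly zero an ordinary two-proportion test gives about 90% for ED visits, so a shortfall there arises only on 2 df.

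The effect on the pilot is limited, because its stated purpose is field testing and estimation. The sentences are nevertheless wrong as written for the rates given, and are worth correcting.

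**What to change.** In Statistical Power and Sample Considerations, either delete the two power sentences or restate them with:
- the rates compared in each case;
- sidedness;
- the cluster coefficient and design effect;
- the assumed test and its degrees of freedom;
- the number of children per site actually taking penicillin.

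If 2-df figures are quoted, the Data Analysis Plan should name the matching analysis. Add that the pilot is not powered for between-group tests, and that power for the future cluster trial will be calculated from the number of sites, using a t distribution on (sites - 2) degrees of freedom.

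This is wording only, with no added sites or families. The cost is that the stated power becomes much less favourable.

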*child health are also currently unknown.* Understanding the processes linking SDoH interventions and health outcomes has the dual benefit of contributing to our scientific knowledge of SDoH and informing treatment targets in future intervention studies. Since SDoH burden falls disproportionately on those with lower socioeconomic status and on racial/ethnic minority families, it will be critical to examine these processes within diverse samples. Given the significance of this emerging field, the NIH is convening a workshop on SDoH screening and referral interventions and its future research directions in May 2018.

**Children with sickle cell anemia are the ideal population in which to study how SDoH interventions may improve health.** Sickle cell disease affects approximately 100,000 people in the US, primarily those of African and Hispanic descent. Sickle cell anemia (SCA) is the most severe form and represents approximately 60% of the sickle cell population. Manifestations of SCA, including sepsis and painful vaso-occlusive episodes, begin in infancy and expected survival is approximately 45 years, nearly 30 years less than for African Americans overall. Use of daily antibiotic prophylaxis in children with SCA until age 5 years reduces mortality, especially in early infancy. Guidelines also recommend that hydroxyurea (HU) be offered to children with SCA beginning at 9 months of age. *However, adherence to therapies proven effective for SCA is low.* One study of >2,800 eligible children with SCA found that only 18% had prescriptions filled for antibiotic prophylaxis for  $\geq 300$  days, far short of the recommended daily intake. In addition, a study of a state Medicaid program showed that only 41% of children prescribed HU were adherent, defined as supplied (from pharmacy records) to cover at least 80% of days in a year. A recent meta-analysis found mixed findings regarding the possible mechanisms underlying low rates of medication adherence among children with sickle cell disease, with medication barriers (e.g., competing demands) having the strongest effect size.

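### The stated 90% power for a 20-point difference in penicillin adherence is reached only with an unexplained 10% control rate, a one-sided test and no allowance for clustering; the protocol's only prophylaxis rate is 18%

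*Combined protocol and SAP*

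**What the plan says.** The section Statistical Power and Sample Considerations (Aim 2) uses two examples to show that the design is feasible: emergency department visits, which is the primary outcome, and penicillin adherence. It plans 35 families at each of four sites, two sites per arm. The common inputs are given as "Assuming a 5% error rate" and "we expect a cluster coefficient no larger than 0.01". For adherence it says that "based on estimates from the literature we expect a 9-month medication adherence of 40% and 10% in the intervention and control groups, respectively". It then claims 90% power for a difference of at least 20% in penicillin adherence, which it regards as clinically meaningful. The adherence sentence has no citation, does not say what counts as adherent, and does not say whether the test is one- or two-sided.

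Background and Significance reports one usual-care rate for prophylaxis: a study of more than 2,800 eligible children "found that only 18% had prescriptions filled for antibiotic prophylaxis for" 300 days or more.

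The power section adds that the pilot will not be used to determine efficacy, and that control-group estimates will be the basis for powering the later trial.

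**The concern.** The planning rate of 10% is well below the only prophylaxis rate that the protocol reports, and nothing explains the gap. The direction matters. For a fixed 20-point difference with control rates in this range, a lower control rate means smaller binomial variance and so higher calculated power. A reader cannot tell whether the 10% comes from a different definition, period or population, or was simply the more convenient value.

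At stake is whether the sample can detect the difference that the plan itself calls meaningful. If the detectable difference is really in the mid or upper twenties, the feasibility statement is too favourable, and a planner of the later trial who reuses the 10% starts from an unsourced figure.

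**Working it through.** **Inputs.** Children per arm: 2 × 35 = 70. Error rate 5%, sidedness not stated, so both are tried. Cluster coefficient 0.01, so the design effect is 1 + (35 − 1) × 0.01 = 1.34 and the effective size is 70 / 1.34 = 52.2 per arm. Control rate p0 = 10% (power section) or 18% (Background and Significance). Intervention rate p1 = p0 + 20 points. No dropout is applied, because the power text gives no rate.

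**Formulas.** With d = p1 − p0 and p̄ = (p0 + p1)/2:

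- SE0 = √[2p̄(1 − p̄)/n]
- SE1 = √{[p0(1 − p0) + p1(1 − p1)]/n}
- pooled power = Φ[(d − z·SE0)/SE1]
- unpooled power = Φ(d/SE1 − z)
- z = 1.96 two-sided, 1.645 one-sided

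Ranges below run from the pooled to the unpooled result.

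**Step 1: the plan's own figure (10% vs 30%).**

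- n = 70: SE0 = 0.0676, SE1 = 0.0655. Two-sided: (0.20 − 1.96 × 0.0676)/0.0655 = 1.03, giving 84.9%; unpooled 0.20/0.0655 − 1.96 = 1.095, giving 86.3%. One-sided: 91.2–92.1%.
- n = 52.2: SE0 = 0.0783, SE1 = 0.0758. Two-sided: 0.615 and 0.679, giving 73.1–75.1%. One-sided: 82.7–84.0%.

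The 90% appears only one-sided with clustering ignored.

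**Step 2: the same difference at 18% (18% vs 38%).**

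- n = 70: SE0 = 0.0759, SE1 = 0.0740. Two-sided: 0.693 and 0.743, giving 75.6–77.1%. One-sided: 84.5–85.5%.
- n = 52.2: SE0 = 0.0879, SE1 = 0.0856. Two-sided: 0.325 and 0.375, giving 62.7–64.6%. One-sided: 74.2–75.5%.

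No combination reaches 90%.

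**Step 3: difference detectable with 90% power, two-sided** (solving the same formulas for d).

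| Control rate | No clustering | Coefficient 0.01 |
|---|---|---|
| 10% | 21.4–22.0 points | 25.3–26.2 points |
| 18% | 24.2–24.8 points | 28.2–29.1 points |

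**Step 4: what drives the shortfall** (pooled, two-sided unless stated).

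- One-sided to two-sided at 10%, no clustering: 91.2% to 84.9%, about 6 power points.
- Adding the design effect at 10%: 84.9% to 73.1%, about 12.
- Moving from 10% to 18%: 84.9% to 75.6% without clustering and 73.1% to 62.7% with it, about 9 and 10. The detectable difference rises by about 3 points either way.

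**Step 5: the penicillin denominator.** Eligibility is daily penicillin or hydroxyurea, and the share on penicillin is not given. As an assumption for illustration only, suppose half take it: 17.5 per site, design effect 1 + 16.5 × 0.01 = 1.165, effective size 35/1.165 = 30.0 per arm. The detectable difference becomes about 34–36 points at 10% and 37–39 at 18%.

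**The case against.** Three arguments on the other side have force.

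*The two rates may not measure the same thing.* The 18% counts children with 300 or more days filled; the 10% is a 9-month figure with no stated threshold. The plan attributes it to the literature, and the reference list includes a study of pneumococcal prophylaxis in publicly insured children that is not cited in the text available here. That study may be the source, though the documents do not say so. A reader might infer that 10% is an error and that 18% should replace it. The documents do not support that; they support only a request to cite, define and reconcile.

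*The control rate is not the main cause.* A reader might infer that the 20-point claim rests on the favourable 10%. It does not: two-sided, the claim already fails at 10%, and the design effect alone costs slightly more power than the move to 18%.

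*The expected effect is larger than 20 points.* At 40% vs 10%, two-sided power with clustering is 95.4–96.5%. This is fair, but the claim under review is the one for 20 points. At 40% vs 18% power is 82.5–84.1% without clustering and 70.3–72.4% with it.

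A further reading is tempting: Background and Significance also "showed that only 41% of children prescribed HU were adherent", which is above the 40% assumed under intervention, so a reader might conclude that no gain is expected for children on hydroxyurea. That does not follow. The power section names penicillin as its example and states the detectable difference for penicillin; the looser mention of medication adherence sits between those two statements. The hydroxyurea rate is not a comparator here.

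**Conclusion.** The point holds as an unexplained inconsistency joined to a power figure that is not reproduced under a two-sided test or with the plan's own clustering. Two-sided, power for 20 points is 85–86% (10%) or 76–77% (18%) without clustering, and 73–75% or 63–65% with it. The control rate accounts for about 9 to 11 of those power points; sidedness and clustering account for the rest.

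These results read adherence as a proportion of children and the 20% as percentage points, and they assume 70 children per arm on penicillin with no losses. They use a normal approximation, which is generous with only two sites per arm. The consequence is modest: penicillin adherence is an illustrative example, the pilot will not determine efficacy, and no sample size or analysis depends on the figure.

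**What to change.** In Statistical Power and Sample Considerations:

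1. Cite the source of the 10% and define adherence at 9 months (measure and threshold).
2. Say why it differs from the 18% in Background and Significance, or show both rates side by side.
3. State whether the 5% is one- or two-sided, and give the design effect of 1.34.
4. Replace the 20-point figure with the difference detectable at 90% power, two-sided: about 25–26 points at 10% and 28–29 at 18% with a cluster coefficient of 0.01 (about 21–22 and 24–25 without clustering).
5. Add that these figures assume all 70 children per arm take penicillin, and restate them once the expected share is known.

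The cost is wording and a less favourable stated figure. No extra patients are needed.
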